## 2 LIST OF ABBREVIATIONS

ADCC	Antibody-Dependent Cellular Cytotoxicity
AE	Adverse Event
AESI	Adverse Event of Special Interest
ALT	Alanine Aminotransferase
ANC	Absolute Neutrophil Count
AST	Aspartate Aminotransferase
BDI-II	Beck depression inventory II
Beta-HCG	Beta Human Chorionic Gonadotropin
BeV	Bevacizumab
CAP	College of American Pathologists
CBC	Complete Blood Count
CFR	Code of Federal Regulations
CLIA	Clinical Laboratory Improvement Amendments
CMP	Comprehensive Metabolic Panel
CPC	Cancer Protocol Committee
CR	Complete Response
CRF	Case Report Form
CT	Computed Tomography
CTCAE	Common Terminology Criteria for Adverse Events
DCI	Duke Cancer Institute
dL	Deciliter
DLP	Data Lock Point
DLT	Dose Limiting Toxicity
DSMB	Data and Safety Monitoring Board
DSMP	Data and Safety Monitoring Plan
DSUR	Development Safety Update Report
DUHS	Duke University Health System
EGFRwt	Epidermal Growth Factor wild type
EGFRvIII	Epidermal Growth Factor variant type III
ESCC	Esophageal Squamous Cell Carcinoma
FACIT-Fatigue	Functional Assessment of Cancer Therapy-Fatigue (FACIT-Fatigue) subscale
FACT-BR	Functional Assessment of Cancer Therapy-Brain
FDA	Food and Drug Administration
FISH	Fluorescence in situ hybridization
GBM	Glioblastoma
Gd-DTPA	Gadolinium-diethylene Triamine Pentaacetic Acid
GCP	Good Clinical Practices
GMP	Good Manufacturing Practices
H&P	History & Physical Exam
HRPP	Human Research Protections Program
HRQoL	Health Related Quality of Life
ICS	Investigational Chemotherapy Service
IHC	Immunohistochemistry
IND	Investigational New Drug
IRB	Institutional Research Board
IV (or iv)	Intravenously
KPS	Karnofsky Performance Status
MAb	Monoclonal Antibody
mCRC	Metastatic Colorectal Cancer
MedDRA	Medical Dictionary for Regulatory Activities
MG	Malignant Glioma

Mg	Magnesium
mg	Milligram
mL	Milliliter
mM	Millimolar
MRI	Magnetic Resonance Imaging
NSCLC	Non-small Cell Lung Cancer
OARC	Office of Audit, Risk, and Compliance
OS	Overall Survival
PD	Progressive Disease
PFS	Progression Free Survival
PFS6	Progression Free Survival at 6 months
p.o.	per os/by mouth/orally
PR	Partial Response
PRO	Patient-Reported Outcome
PRTBTC	Preston Robert Tisch Brain Tumor Center
PT	Prothrombin Time
PTT	Partial Thromboplastin Time
RDSPs	Research Data Security Plans
RR	Response Rate
SCCHN	Squamous Cell Carcinoma of the Head and Neck
SD	Stable Disease
SGOT	Serum Glutamic Oxaloacetic Transaminase
SOC	Safety Oversight Committee
ULN	Upper Limit of Normal
WHO	World Health Organization
XRT	Radiation Therapy

## 3 PROTOCOL SYNOPSIS AND RESEARCH SUMMARY

### 3.1 Purpose

The purpose of this study is to assess the activity of Sym004, a recombinant antibody mixture that specifically binds to EGFR, in patients diagnosed with recurrent glioblastoma whose tumor is EGFR amplified.

#### Primary Objective:

Assess the activity of Sym004 in patients with recurrent glioblastoma that are either non-bevacizumab failures (Cohort 1) or who have previously failed bevacizumab (Cohort 2), in terms of 6-month progression-free survival (PFS6).

#### Secondary Objectives:

1. Determine the safety of Sym004 in recurrent GBM patients.
2. Estimate response rate (RR) within the two cohorts of recurrent GBM patients.
3. Describe overall survival (OS) within the two cohorts of recurrent GBM patients.

#### Exploratory Objectives:

1. Assess the impact of EGFRvIII expression on efficacy (OS and PFS) of Sym004.
2. Describe patient-reported quality of life outcomes.

#### Hypothesis

This study hypothesizes that Sym004 will have greater activity in terms of PFS6 than standard treatment for patients with recurrent GBM.

### 3.2 Design and Procedure

This is a phase 2 study that will accrue patients with WHO grade IV recurrent malignant glioma (glioblastoma or gliosarcoma) in two cohorts to assess the efficacy of Sym004. Cohort 1 will include patients who are non-bevacizumab failures; whereas, Cohort 2 will include patients who have progressed after prior treatment with bevacizumab (bevacizumab-failure). Both cohorts will accrue simultaneously, with 36 subjects in Cohort 1 and 25 subjects in Cohort 2 (see Section 13.8 for justification of sample size). All patients will be treated with Sym004, a recombinant antibody mixture that specifically binds to EGFR. For that reason, only patients whose tumor is determined to be EGFR-amplified (i.e. greater than 15% of cells exhibiting > 5 copies of EGFR loci) will be accrued on this study.

Prior to Amendment 31, approximately 25 subjects received Sym004 at 18 mg/kg intravenously every two weeks. After the approval of Amendment 31, subjects who enroll on study will receive Sym004 at 24 mg/kg intravenously every 2 weeks. A total of 65 additional subjects (36 in Cohort 1 and 29 in Cohort 2) will be treated at the 24 mg/kg dose level. In addition, subjects who enrolled at the 18 mg/kg dose and who tolerated this dose of Sym004 well (i.e. no skin toxicities  $\geq$  grade 3) will have the option to increase their dose to 24 mg/kg upon approval of Amendment 31. A treatment cycle will be 4 weeks. The patients will have repeat MRIs of the brain every 8 weeks.

The accrual of the first 3-6 patients at the 24 mg/kg dose level, regardless of cohort assignment, will be at a controlled rate for initial safety monitoring. Details concerning this initial accrual at the 24 mg/kg dose level can be found in Section 13.7.4.

For an exploratory objective, we will determine EGFRvIII status at baseline for all patients using archival tumor tissue. If a subject has more than one source of archival or frozen tissue, each source may be requested to determine if EGFRvIII expression has changed over time.

### 3.3 Selection of Subjects

Selection of subjects will be completed by meeting the subject eligibility criteria listed in this section.

Inclusion Criteria (answer must be YES to all criteria listed below)

1. Patients must have histologically confirmed diagnosis of WHO grade 4 malignant glioma and radiographic evidence of recurrence or disease progression (as defined by the RANO criteria as a greater than 25% increase in the largest bi-dimensional product of enhancement or a new enhancing lesion, or a significant increase in T2/FLAIR abnormality without another co-morbid cause);
2. Age  $\geq$  18 years;
3. Karnofsky Performance Status  $\geq$  70%;
4. No more than 3 prior progressions;
5. Cohort 1 only: Non-bevacizumab failure, i.e. either no prior bevacizumab or bevacizumab stable/responder, which is defined as stable for at least 6 months from prior treatment with bevacizumab without experiencing a bevacizumab adverse event of special interest (AESI) while on a bevacizumab-containing regimen, such as:
  - a.  $\geq$  grade 3 hypertension not controlled by medication, hypertensive crisis, or hypertensive encephalopathy
  - b.  $\geq$  grade 3 proteinuria that does not resolve or nephrotic syndrome
  - c. Any grade GI perforation
  - d.  $\geq$  grade 3 infusion-related reaction
  - e.  $\geq$  grade 3 wound healing complications
  - f.  $\geq$  grade 3 hemorrhage or any grade CNS hemorrhage or  $\geq$  grade 2 hemoptysis
  - g. Any grade arterial thromboembolic event (e.g. myocardial infarction or cerebral infarction) or  $\geq$  grade 3 venous thromboembolic event
  - h. Any grade posterior reversible encephalopathy syndrome (PRES)
  - i.  $\geq$  grade 3 congestive heart failure
  - j.  $\geq$  grade 2 non-gastrointestinal (GI) abscesses and fistulae;
6. Cohort 2 only: Prior progression on a bevacizumab-containing regimen (defined as having progressed/grown through bevacizumab by RANO criteria within 2 months of prior bevacizumab treatment);
7. Pathology consistent with EGFR-amplification of tumor (i.e. greater than 15% of cells exhibiting  $> 5$  copies of EGFR loci); archival tissue may be tested for EGFR status in a separate consent;
8. ANC  $\geq$  1,000 cells/ $\mu$ l, platelets  $\geq$  100,000 cells/ $\mu$ l, hemoglobin  $\geq$  9 g/dL;
9. Adequate renal function as indicated by the following:
  - a. Serum creatinine  $\leq$  1.25 times upper limit of normal or calculated creatinine clearance  $\geq$  50 ml/min;
  - b. Urine dipstick for proteinuria  $< 2+$  unless a 24-hour urine protein  $< 1$  g of protein is demonstrated;
10. Adequate liver function as indicated by the following:
  - a. Total bilirubin  $\leq$  1.6 mg/dL;
  - b. AST/ALT  $\leq$  2.5 x the ULN;
11. Magnesium  $\geq$  0.9 mg/dL;
12. For subjects on corticosteroids, they must be on a stable dose for *7 days* prior to anticipated start of study drug;
13. No evidence of  $>$  grade 1 active CNS hemorrhage on the baseline MRI or CT scan;
14. Signed informed consent approved by the Institutional Review Board prior to patient entry;
15. If the patient is a sexually active female of child bearing potential whose partner is male, or if the patient is a sexually active male whose partner is a female of child bearing potential, the patient must agree to use appropriate contraceptive measures for the duration of the treatment of the tumor and for 6 months afterwards as stated in the informed consent. Female patients of child bearing potential must have a negative serum pregnancy test within 48 hours of starting study treatment;

16. Fertile male subjects must agree to use a medically acceptable contraceptive method (allowed methods of birth control include vasectomy or condom with spermicide) during the trial and for a period of at least 6 months following the last administration of trial drugs.

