## 10 SCREENING AND ON-STUDY TESTS AND PROCEDURES

		Time Points								End of Treatment
		Cycle 1		Cycle 2		Cycle 3		Cycle 4...		
Evaluation	Screening a	Day 1	Day 15	Day 1	Day 15	Day 1	Day 15	Day 1	Day 15	
Informed consent	X									
Determination of EGFR amplification b	X									
History and complete physical exam, including full neurologic exam & KPS	X					X				X
Interval history and brief physical exam		X c	X	X	X		X	X	X	
Vital signs, including blood pressure and weight; calculate BMI d	X	X c	X	X	X	X	X	X	X	X
CBC with differential e	X		X	X	X	X	X	X	X	X
CMP + Mg e	X		X	X	X	X	X	X	X	X
Urinalysis	X									
Beta-HCG, if applicable, within 48 hours prior to start of study treatment, if contraception not initiated at time of negative test result prior to that time	X									
MRI of the brain f	X					X				X
Determination of EGFRvIII from archival tumor tissue g	X									
Quality of life measurements h	X					X				X
Skin toxicity assessment i	X		X	X	X	X	X	X	X	X
Toxicity assessment		Ongoing								
Pre-medication j		X								
Sym004 infusion		X	X	X	X	X	X	X	X	

a Within 2 weeks prior to first dose of Sym004. Some tests and procedures (as noted) are for a baseline only, not for eligibility.

b Determination of EGFR amplification may be taken from the original pathology diagnosis or maybe be tested from archival tissue as a part of screening by FISH (separate consent).

c Interval history with brief physical exam, vital signs, blood pressure, and weight do not need to be repeated if the screening exam and vitals occurred within 3 days of Day 1.

dBMI must be calculated before every infusion.

e Every 2 weeks, beginning with Cycle 1:Day 15.

f MRIs will be obtained every 8 weeks (i.e. every other cycle), prior to the start of the next cycle.

g EGFRvIII expression will be determined at baseline using archival tumor tissue; however, if a subject has more than one source of archival or frozen tissue, each source may be requested to determine if EGFRvIII expression has changed over time. EGFRvIII expression will be determined using IHC by the Duke Department of Pathology if not previously obtained.

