## **10.4 Re-treatment Criteria (day 1 and day 15)**

Subjects must meet the following re-treatment criteria prior to infusion with Sym004, in order to receive the next scheduled infusion. Dose modifications are allowed as described in Section 7.1.1.

- ANC  $\geq$  1,000 cells/ $\mu$ l
- Platelets  $\geq$  50,000 cells/ $\mu$ l
- AST, bilirubin, creatinine  $\leq$  2.0 x upper limit of normal
- Resolution of any grade 3 or greater toxicity felt to be possibly, probably or definitely attributable to the study regimen to grade 2 or lower based on the investigator's decision.

If treatment with Sym004 is delayed for longer than 2 weeks due to toxicities (i.e. grade 3-4 non-hematologic toxicities secondary to Sym004, such as skin toxicities, electrolyte disturbances, and gastrointestinal symptoms, or grade 4 neutropenia or thrombocytopenia), the MRI assessment that would normally occur prior to beginning a new cycle or at the end of treatment will still be obtained no later than  $8 \pm 2$  weeks after the previous MRI assessment. Once the toxicities have resolved to meet re-treatment criteria, the subject will resume Sym004. The day Sym004 is resumed will be considered Day 1 of the next cycle expected for the subject, which means that we will omit day 15 infusion for the previous cycle.

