### 10.9.6 Laboratory Evaluations

The timing of laboratory assessments that will be obtained during the course of the study is given in Section 10. A list of each evaluation and what they include, when done at a Duke facility, is below.

- CBC with differential (hematocrit, hemoglobin, platelet count, white blood cell count, mean corpuscular volume, mean corpuscular hemoglobin, mean corpuscular hemoglobin concentration, NRBC %, NRBC CT, RDW-CV, absolute lymphocyte count, percent lymphocytes, percent monocytes, percent neutrophils, percent eosinophils, percent basophils, absolute monocyte count, absolute neutrophil count, absolute eosinophil count, absolute basophil count, red blood cell count)
- CMP + Mg (albumin, alanine aminotransferase, alkaline phosphatase, aspartate aminotransferase, total bilirubin, total protein, calcium, potassium, sodium, carbon dioxide creatinine, urea nitrogen, glucose, chloride + magnesium)
- Beta-HCG, if applicable, within 48 hours prior to start of study treatment

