### 13.1 Analysis Sets

Safety and efficacy analyses will include all patients who received any Sym004 treatment.

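### An eligible patient whose AST stays above 2.0 and up to 2.5 x ULN gets dose 1 and is then held from Cycle 1 Day 15, because the re-treatment limit is tighter than the entry limit (minor dosing-rule mismatch)

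*Combined protocol and SAP*

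**What the plan says.** Section 3.3, inclusion criterion 10b, sets the entry limit: "AST/ALT $\leq$ 2.5 x the ULN". Section 10.4, which covers Day 1 and Day 15 infusions, lists "AST, bilirubin, creatinine $\leq$ 2.0 x upper limit of normal" among its conditions and makes the list mandatory: "Subjects must meet the following re-treatment criteria prior to infusion with Sym004, in order to receive the next scheduled infusion".

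In the section 10 schedule, chemistry is drawn at screening and then, per table note e, "Every 2 weeks, beginning with Cycle 1:Day 15". The panel includes AST; section 10.9.6 lists it as "CMP + Mg (albumin, alanine aminotransferase, alkaline phosphatase, aspartate aminotransferase". No chemistry is scheduled on Cycle 1 Day 1.

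The blood-count limits do not tighten after entry. ANC is at least 1,000 at both points. Platelets go from "platelets $\geq$ 100,000 cells/ $\mu$ l" at entry to "Platelets $\geq$ 50,000 cells/ $\mu$ l" at re-treatment.

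Section 13.1 keeps every treated patient in the analysis: "Safety and efficacy analyses will include all patients who received any Sym004 treatment". Section 10.8.3 replaces early withdrawals only if they never started Sym004. Section 13.7.4 sets a minimum of two full doses in Cycle 1 for the first patient at 24 mg/kg.

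**The concern.** A patient may start treatment at an AST level that then bars the second dose. No reason is given for a tighter limit on re-dosing than on first dosing. Whichever limit was intended, the pair does not fit together: either 10b admits patients whom the sponsor would not want to re-dose, or 10.4 holds patients whom the sponsor meant to treat.

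The main stake is the individual patient with recurrent glioblastoma, who would miss scheduled treatment with no worsening and no attribution to Sym004. That patient still counts in the efficacy and safety sets after a single dose and is not replaced. There is also a narrow operational stake at the start of 24 mg/kg dosing, where the first patient must complete two doses before a second patient is accrued.

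**Working it through.** **Step 1: the limits side by side.**

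| Parameter | Entry (3.3) | Re-treatment (10.4) | Direction |
|---|---|---|---|
| AST | up to 2.5 x ULN | up to 2.0 x ULN | tighter |
| ALT | up to 2.5 x ULN | not listed | no limit |
| ANC | at least 1,000 | at least 1,000 | same |
| Platelets | at least 100,000 | at least 50,000 | looser |
| Serum creatinine (serum route) | up to 1.25 x ULN | up to 2.0 x ULN | looser |

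Bilirubin is in mg/dL at entry and in multiples of ULN at re-treatment, so the two cannot be compared without the laboratory's ULN. The mismatch described here concerns AST only.

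**Step 2: a patient in the gap.** Take a stable AST of 2.3 x ULN. At screening 2.3 is below 2.5, so the patient is eligible. Dose 1 goes ahead on that value. At Cycle 1 Day 15, 2.3 exceeds 2.0, so dose 2 is withheld, and so is each later dose while AST stays there.

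**Step 3: is there a clause that releases the patient?** I found none.
- The investigator's discretion in 10.4 belongs to the item on attributable grade 3 or higher toxicity, not to the AST limit.
- 10.4 refers to 7.1.1 for dose modification. Sections 7.1.1 and 7.1.2 reduce the dose for grade 3-4 toxicity and do not relax the AST limit.
- The long-delay and resumption text in 10.4 is written for delays caused by toxicity and does not address a stable pre-existing elevation.

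**Step 4: how many patients?** The documents give no frequency. Let f be the fraction *entering* with AST above 2.0 and up to 2.5 x ULN, assumed to be 0.01, 0.02 or 0.05. The planned maximum at 24 mg/kg is 36 + 29 = 65. The smallest total, if both cohorts stop after stage 1, is 19 + 12 = 31.

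| | f = 0.01 | f = 0.02 | f = 0.05 |
|---|---|---|---|
| Expected entering the band, 65f | 0.65 | 1.3 | 3.25 |
| At least one held, all persist, 1 - (1 - f)^65 | 0.48 | 0.73 | 0.96 |
| At least one held, half persist, 1 - (1 - f/2)^65 | 0.28 | 0.48 | 0.81 |
| At least one held, all persist, only 31 treated, 1 - (1 - f)^31 | 0.27 | 0.47 | 0.80 |

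The chance that the first 24 mg/kg patient enters in the band is f itself: 0.01, 0.02 or 0.05.

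**Step 5: effect on PFS6.** The Cohort 1 design (13.8.2) treats 19 patients, continues if more than 3 succeed, treats 36 in total and succeeds if more than 10 do. Its success probability is the sum over x = 4 to 19 of Bin(x; 19, p) x P(Bin(17, p) > 10 - x).

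Reproducing the plan: p = 0.20 gives 0.0861 (stated type I error 0.086) and p = 0.40 gives 0.9024 (stated type II error 0.098, so power 0.902).

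For Cohort 2 I compute only the chance of passing stage 1, 1 - (1 - p)^12, which is 0.931 at p = 0.20.

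The worst case assumes that all patients in the band are held permanently and have null PFS6: p = 0.40(1 - f) + 0.20f in Cohort 1 and 0.20(1 - f) + 0.03f in Cohort 2. The half-effect case assumes that held patients keep half the gain, so 0.30 replaces 0.20 and 0.115 replaces 0.03.

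| | f = 0 | f = 0.01 | f = 0.02 | f = 0.05 |
|---|---|---|---|---|
| Cohort 1 power, worst case | 0.902 | 0.898 | 0.894 | 0.880 |
| Cohort 1 power, half effect | 0.902 | 0.900 | 0.898 | 0.892 |
| Cohort 2 stage 1, worst case | 0.931 | 0.930 | 0.928 | 0.922 |
| Cohort 2 stage 1, half effect | 0.931 | 0.930 | 0.930 | 0.927 |

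The largest loss in Cohort 1 is 0.902 - 0.880 = 0.022. If holds lift at the next two-weekly check, the loss is close to none.

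**The case against.** The best defence is that entry and re-treatment limits answer different questions: who may start, and whether another infusion is safe now. Section 10.4 applies one ceiling to AST, bilirubin and creatinine, which could be a deliberate organ-function limit. Both rules can be obeyed as written, and the documents do not show which limit is the wrong one. That stands, and it is why two alternative fixes are offered. It does not remove the mismatch: if 2.0 x ULN is the safety limit for a further dose, the plan gives no reason for starting patients above it.

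The frequency is also open to challenge. The 1% to 5% range is an assumption and counts patients entering the band, whereas the harm needs AST to remain above 2.0 x ULN at Day 15. In addition, 65 is a maximum. Both points stand, so the all-persist rows in Step 4 are upper bounds for a given f.

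Three stronger readings are tempting, and the documents do not support them.
- A reader might infer that the rules contradict each other or that 2.0 is a typing error. Nothing in the text shows either.
- A reader might infer that the first safety look at 24 mg/kg would rest on a single dose. Section 13.7.4 requires two full doses from the first patient, so one dose would not complete that step. The likelier result is a delay or a query. The minimum is stated for the first patient only. A patient escalated from 18 mg/kg may also count among the first three; already subject to the 10.4 check, such a patient is unlikely to be newly caught.
- A reader might infer damage to the primary analysis. Step 5 shows otherwise, even in the worst case.

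**Conclusion.** The mismatch is real and minor. The two thresholds, the mandatory wording, the lack of a baseline exemption and the Day 15 timing are all plain in the text, and confidence in them is high. A patient who stays above 2.0 and up to 2.5 x ULN gets one dose and is then held until a later value is 2.0 x ULN or lower.

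Confidence in the size is lower, because it rests on the assumed entry fraction and on how often AST stays raised; the documents inform neither. Within that range the effect on PFS6 inference is negligible, and no sample size, boundary or analysis needs to change. The case for correcting it rests on the individual patient's dosing and on avoiding a possible stall at the first 24 mg/kg patient.

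**What to change.** Align the two limits in the next amendment, by one of two routes.

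1. **If 2.0 x ULN is the intended safety limit:** lower the AST limit in 10b to 2.0 x ULN. The cost is a few lost candidates, about 0.65 to 3.25 per 65 under the assumed 1% to 5%.
2. **If patients up to 2.5 x ULN are meant to be treated:** add to 10.4, for AST only, that patients who entered above 2.0 x ULN may be re-treated at AST up to 2.5 x ULN. The cost is continued dosing at a stable elevation, or after a rise that stays within the 2.5 x ULN cap.

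Under either route, keep 2.0 x ULN in 10.4 for all other patients. Raising it for everyone would allow re-dosing after an on-drug rise, at a dose that 13.7.4 describes as having limited prior experience. An exemption tied to the patient's own baseline value would work poorly: a stable patient at 2.30 x ULN who reads 2.32 on Day 15 would still be held, and with symmetric variation around a stable level about half of checks would exceed baseline.

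The edit is one line and adds no tests, since the two-weekly panel already reports AST. Under 14.7 it needs IRB approval, and the Cancer Protocol Committee should be informed.

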## 10.1 Screening Examination

If a candidate subject does not have EGFR status in his or her medical records, EGFR and EGFRvIII status may be tested from that patient's archival biopsy. The subject must sign a tissue screening consent before this can take place.

The screening examinations and procedures will take place within 2 weeks of starting study drug treatment. An informed consent must be signed by the patient before any research-related screening procedure takes place.

If screening occurs within 3 days of first study drug infusion, the screening tests can be used as Cycle 1 Day 1 examinations. Pre-treatment evaluations to determine eligibility are listed in the schema above and include the following:

- History and full physical exam, including a full neurologic assessment and KPS, two weeks prior to starting treatment
- Vital signs, including blood pressure and weight
- CBC with differential, CMP+Mg, Beta-HCG if appropriate (within 48 hours of beginning study drug if contraception not initiated at time of negative test result prior to that time)
- Urinalysis
- Baseline MRI of the brain 2 weeks prior to starting treatment
- Determination of EGFRvIII from archival tumor tissue
- Skin assessment, as a baseline measurement
- Quality of life measurements, as a baseline measurement
- Determination of EGFRvIII amplification

If a subject is found to be ineligible to participate in the study, minimal records regarding the subject and the reason for screen failure will be retained in the study database.

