**1. Determine Patient Background Information**

- A. Determine the patient's medical history.
- B. Has the patient had prior surgery?

C. Has the patient had Gliadel (carmustine) wafers placed into the resection cavity? Note: Be careful with therapeutic effect

D. Has the patient undergone radiation therapy or stereotactic radiosurgery?

Note: Be careful with pseudoprogression

E. Has the patient taken any anti-angiogenic agents, such as bevacizumab (Avastin), sunitinib (Sutent), or cediranib (Recentin)? Note: Be careful with pseudoresponse and non-enhancing disease progression

F. Has the patient experienced seizure activity recently?

G. Has the patient tapered up or down in their dose of steroids? H. Has the patient undergone any form of immunotherapy?

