**2. Pick the right date of previous MRI/CT to which you want to compare the new MRI**

- A. For high grade patients off therapy, go back to the MRI when they stopped therapy.
- B. For low grade patients off therapy, go back to baseline MRI. The best baseline MRI is normally 2-

4 months post-operative (post-operative changes must have resolved and at the nadir of cavity collapse).

[figure not shown]
C. For patients on treatment, compare to baseline (response) and to nadir (progression).

[figure not shown]

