**T1 pre contrast**

**T1 post contrast**

- C. Pick target lesion.
  - i. Some lesions are followed quantitatively, some qualitatively.
  - ii. Measurable lesions are those that you COULD follow quantitatively
  - iii. Target lesions are those that you WILL follow quantitatively
  - iv. Only enhancing lesions can be quantitative.
- D. Measurable lesions must have the following criteria:
  - v. Contrast enhancing
  - vi. Clearly defined, bi-dimensionally measurable margins
  - vii. Two perpendicular diameters  $\geq 10\text{mm}$
  - viii. If slice thickness + gap is  $>5\text{mm}$ , size threshold is 2 x total
  - ix. Do not include surgical cavity, cyst, or necrotic area
- E. Non-measurable lesions meet the following criteria:
  - x. Less than 1 cm in any diameter (e.g.  $12 \times 8\text{ mm}$ )
  - xi. Poorly defined margin
  - xii. Hemorrhagic or predominantly necrotic
  - xiii. Tumor around a cyst or surgical cavity, unless nodular component  $\geq 10 \times 10\text{ mm}$
- F. Choosing target lesions:
  - xiv. If there is more than one, pick up to 5.
  - xv. Choose the largest lesions.
  - xvi. Should have reproducible measurement.

G. Determine RANO – Target lesion measurement/response

- i. Axial plan is recommended, unless patient has been followed in coronals
- ii. Pick the slice where the lesion is the largest
- iii. Measure the longest diameter (A)
- iv. Next, measure the greatest perpendicular diameter (B)
- v. Calculate the target lesion size - product of the diameters (AXB)
- vi. With multiple target lesions, calculate the sum of the product of the diameters  

$$(SPD) = \text{Area001} + \text{Area002}$$
- vii. Follow-up evaluation:
  - a. Measure the previously defined target lesions bi-dimensionally and calculate the SPD (Note: CR and PR have to be confirmed  $\geq 4$  weeks later; otherwise, it's just SD)
  - b. If apparent PD within 12 weeks of radiation, keep watching. If SPD stable or decreased on next visit, drop baseline value when picking "nadir" to compare against.
  - c. Are there new lesions?

H. RANO – Enhancing non-target lesion response

- i. All non-measurable lesions
- ii. All measurable lesions beyond upper limit of 5
- iii. All other measurable lesions not selected as target lesion

Response	Definition
Complete Response (CR)	All target lesions have completely disappeared. (look out for pseudoresponse)
Partial Response (PR)	SPD decreased by $\geq 50\%$ from baseline value (look out for pseudoresponse)

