L. RANO – Radiological and clinical factors

Overall Visit Response	Definition
CR	
 
• CR by MRI
 
• No steroids above physiological levels
 
• Clinical status stable or improved compared to baseline
 

PR	
 
• PR by MRI
 
• Steroid dose not increased compared to baseline
 
• Clinical status stable or improved compared to baseline
 

SD	
 
• SD by MRI
 
• Steroid dose not increased compared to baseline
 
• Clinical status stable or improved compared to baseline
 

PD	
 
PD by MRI
 
Steroid dose stable or higher compared to visit at which best MRI response was seen
 
Clinical status worsened compared to either baseline or the visit which showed the best MRI response, and not attributable to a non tumor-related cause
 

NC	
 
NC by MRI (possible only if no visible tumor at baseline)
 
Steroid dose not increased compared to baseline
 
Clinical status stable or improved compared to baseline
 

UA	
 
UA by MRI
 
Steroid dose not increased compared to baseline
 
Clinical status stable or improved compared to baseline
 

M. RANO response criteria

	CR	PR	SD	PD
T1-Gd +	None	$\geq 50\% \downarrow$	$< 50\% \downarrow -$ $< 25\% \uparrow$	$\geq 25\% \uparrow^*$
T2/FLAIR	Stable or <math>\downarrow</math>	Stable or <math>\downarrow</math>	Stable or <math>\downarrow</math>	$\uparrow^*$
New Lesion	None	None	None	Present*
Corticosteroids	None	Stable or <math>\downarrow</math>	Stable or <math>\downarrow</math>	NA
Clinical Status	Stable or <math>\uparrow</math>	Stable or <math>\uparrow</math>	Stable or <math>\uparrow</math>	$\downarrow^*$
Requirement for response	all	all	all	Any*

	CR	PR	SD	PD
T1-Gd +	None	$\geq 50\% \downarrow$	$< 50\% \downarrow -$ $< 25\% \uparrow$	$\geq 25\% \uparrow^*$
T2/FLAIR	Stable or <math>\downarrow</math>	Stable or <math>\downarrow</math>	Stable or <math>\downarrow</math>	$\uparrow^*$
New Lesion	None	None	None	Present*

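### Steroid dose must be stable for 7 days before the first infusion, but the baseline MRI may be up to 14 days before it, and Appendix B does not date the baseline steroid dose

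*Combined protocol and SAP*

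**What the plan says.** **Steroid stability.** Inclusion criterion 12 in Section 3.3 reads "For subjects on corticosteroids, they must be on a stable dose for *7 days* prior to anticipated start of study drug". The 7 days are counted back from the first infusion, and the criterion does not mention the scan.

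**Baseline scan.** The brain MRI is in the screening column of the Section 10 schedule, whose footnote a gives the window as "Within 2 weeks prior to first dose of Sym004". Section 10.1 says generally that "The screening examinations and procedures will take place within 2 weeks of starting study drug treatment", but words the scan itself as "Baseline MRI of the brain 2 weeks prior to starting treatment". Read literally, that last wording puts the scan outside the stable-dose period every time. The more natural reading is any day in the 2 weeks.

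**Use of the scan.** Appendix B, items 2 and 5, measures response from the baseline scan (partial response, PR: SPD down by at least 50%). It measures progressive disease (PD) from the nadir, the smallest value seen in the trial (SPD up by at least 25%).

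**Use of the steroid dose.** Appendix B item L makes PR and stable disease (SD) conditional on "Steroid dose not increased compared to baseline". Item N turns a radiological PR into SD when steroids are up. Item 1 has the reader ask "Has the patient tapered up or down in their dose of steroids". None of these says on which date the baseline dose is taken. The Section 10 schedule has no entry for steroid dose.

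**The concern.** Appendix B treats steroid dose as something that changes how a scan is read. The scan that anchors those readings may nevertheless be taken on a different dose from the one the subject is on at treatment start, and nothing in the plan prevents or records this.

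The baseline scan is the reference for every SPD-based response call. At the first on-study MRI, at 8 weeks, it is also the only available nadir. A steroid increase after the scan can make a tumour look smaller than it is relative to baseline, which favours a response call and delays progression. A reduction does the reverse. SPD-based progression feeds PFS6, the primary endpoint. Separately, an undated baseline steroid dose lets two readers reach different response calls from the same data.

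**Working it through.** The plan states no figure on this point, so there is none to reproduce. The check has four steps.

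**1. The gap.** Scan window 14 days (Sections 10 and 10.1); stable-dose window 7 days (criterion 12). Uncovered period: 14 − 7 = up to 7 days. A subject scanned on day −14 can change dose up to day −8 and meet criterion 12. For a scan in the last 7 days the gap is 0. No section asks for a stable dose at the scan, a repeat scan after a change, or a record of the dose at the scan.

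**2. Effect on the thresholds.** Let a steroid change after the scan shift SPD by a fraction s with no change in tumour, so the size at treatment start is (1 + s) × baseline. While baseline is the nadir:

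- true growth needed for PD = 1.25/(1 + s) − 1
- true shrinkage needed for PR = 1 − 0.5/(1 + s)

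The values of s are assumptions; the documents give none.

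| s | Direction | Growth for PD (nominal 25%) | Shrinkage for PR (nominal 50%) |
|---|---|---|---|
| −20% | increase | 1.25/0.8 − 1 = 56% | 1 − 0.5/0.8 = 38% |
| −10% | increase | 1.25/0.9 − 1 = 39% | 1 − 0.5/0.9 = 44% |
| +10% | reduction | 1.25/1.1 − 1 = 14% | 1 − 0.5/1.1 = 55% |
| +20% | reduction | 1.25/1.2 − 1 = 4% | 1 − 0.5/1.2 = 58% |

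**3. How long the PD effect lasts.** It ends once an on-study scan is smaller than baseline. With s = −20%, a week-8 scan is below baseline whenever true growth is under 1/0.8 − 1 = 25%. That scan becomes the nadir and the ordinary 25% rule applies from then on. The tumours missed at that scan are those with 25–56% growth (25–39% for s = −10%). After a reduction the baseline is artificially low and can stay the nadir. The response effect does not expire, because baseline remains the reference throughout.

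**4. The undated steroid baseline.** Take a subject scanned on day −14, with the dose raised on day −10 and unchanged afterwards.

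| Finding on MRI | Baseline dose = dose at scan | Baseline dose = dose on Day 1 |
|---|---|---|
| SPD meets PR | Steroids are up, so item N gives SD | Steroids are not up, so PR (if confirmed) |
| SPD in SD range, worse at next visit | Item N dates PD to the steroid increase, which read literally precedes treatment | PD is dated to the later worsening |

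The second row also conflicts with Sections 3.4 and 13.5.2, which count PFS from the start of treatment.

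**The case against.** The strongest case against is that the two windows can both be satisfied, so nothing is contradictory, and that the consequence is narrow. Most of the second part stands:

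- Only subjects on steroids, scanned more than 7 days before dosing, whose dose changed in the gap are affected. The documents do not say how many these are.
- PD by new lesion, T2/FLAIR worsening or clinical decline, and death, do not use the baseline SPD.
- Scans are every 8 weeks. After a steroid increase, a PD call delayed from week 8 to week 16 leaves PFS6 status unchanged. A false PFS6 success requires PD to be missed until past 6 months.
- Appendix B has partial safeguards: the steroid conditions in items L and N, confirmation of CR and PR at least 4 weeks later, and the reader's question about tapering. For a reduction, the PD row of item L asks for steroids stable or higher than at the best-response visit, which might block a false PD.

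The safeguards do not close the gap. The steroid conditions catch a rise between scan and Day 1 only if baseline means the dose at the scan. A confirmatory scan is compared with the same baseline. The tapering question carries no rule for this interval. Item M marks steroids as not applicable for PD, so the protection in item L is uncertain.

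A reader might infer that every later response and progression call is distorted. The nadir rule and the other routes to PD rule that out. A reader might also infer that the Cohort 2 stage 1 decision, which continues on more than 0 of 12 successes, is compromised. That rule is sensitive to one patient, but nothing in the documents shows that this gap misclassifies one.

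**Conclusion.** The mismatch is real and nothing in the documents closes it. In subjects on steroids, the dose can change for up to 7 days after the reference scan while eligibility is met. In those subjects, response calls can be biased, as can SPD-based progression calls while the baseline scan is still the nadir. The threshold shifts (39–56% or 14–4% in place of 25%) rest on assumed SPD changes of 10–20% and hold only under that nadir condition. Neither the frequency nor an effect on PFS6 can be derived from the documents.

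The undated baseline steroid dose is a definite gap whatever the frequency, since the two readings can give different response calls for the same patient. The point is a cheap improvement in measurement. It does not invalidate the design and changes no sample size or error rate.

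**What to change.** At the next amendment:

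1. Reconcile criterion 12 with the screening-MRI timing in Sections 10 and 10.1, so that the baseline MRI falls within the stable-dose period. This concerns when the reference scan is taken and should not prescribe how steroids are managed. Settle the wording of the scan timing in Section 10.1 at the same time.
2. Record the steroid dose on the date of the baseline MRI.
3. Define the baseline steroid dose in Appendix B, items L to N, as that dose.

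With the first change in place, the dose at the scan and the dose on Day 1 should normally agree, and the two readings in the working converge.

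Cost: eligibility, schedule and appendix wording, plus one data field. Some baseline scans will have to be booked closer to the first infusion. An occasional patient whose dose changes after the scan may need a repeat scan or be flagged in the response assessment.
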